Given the strong evidence of both safety and efficacy in a related form of heart failure, along with the fact that dapagliflozin is FDA approved for both HFrEF and diabetes, the risk-benefit ratio very much favors benefits in the present study testing DAPA in patients with heart failure and preserved EF.

2 Study Objectives

Primary Objective

To determine whether treatment with DAPA for 6 months will improve pulmonary capillary wedge pressure (PCWP) during exercise in HFpEF.

Secondary Objectives

- 1. To determine whether treatment with DAPA for 6 months can improve myocardial metabolism and substrate utilization, shifting from high uptake of free fatty acids to favor glucose utilization.
- 2. To determine whether treatment with DAPA for 6 months will improve other hemodynamic markers of HF severity (at rest and with exercise) in HFpEF.
- 3. To determine whether treatment with DAPA for 6 months can improve ventricular function and functional reserve as assessed by tissue Doppler echocardiography and strain imaging.
- 4. To determine whether treatment with DAPA for 6 months can reduce plasma volume assessed by labelled albumin indicator dilution technique.

Page 8 of 34

Principal Investigator: [name]

5. To determine whether treatment with DAPA for 6 months can improve exercise capacity and quality of life in HFpEF, and explore how these clinical changes relate to changes in hemodynamics, cardiac function, and cardiac metabolism.

3 Study Design

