3.1 General Description

This is a mechanistic phase II placebo-controlled trial designed to determine whether treatment with dapagliflozin for 6 months will improve exercise hemodynamics, cardiac metabolism, and clinically relevant endpoints in patients with HFpEF.

Brief Synopsis of Methods:

- 1) Enroll subjects with HFpEF. Some patients will have previously been identified and some will have be referred to the catheterization lab for evaluation of dyspnea and suspected HFpEF. The latter patients will only qualify for randomization if they meet hemodynamic entry criteria for HFpEF (PCWP of ≥25 mmHg with exercise).
- 2) Safety lab sampling (complete blood count, creatinine, blood urea nitrogen, sodium, potassium, aspartate aminotransferase, alanine aminotransferase, total, direct and indirect bilirubin) hs-CRP, HgA1c, NTproBNP will be performed. Values may be used up to a week prior to study if the same bloods have already been drawn.
- In the preparation area, an IV cannula will be inserted in a forearm vein for initiation of isotope infusion ([U-13C] palmitate), allowing for attainment of steady-state prior to transfer to the catheterization laboratory (~60 min). Isotope infusions will be continued until blood sampling studies have been completed.
- 4) Assess hemodynamics at rest and during exercise using gold standard invasive techniques in patients with HFpEF. Venous, arterial and coronary sinus blood samples obtained at rest and during exercise. Focused echocardiography examination with measurement of LV and RV tissue Doppler echocardiography and cardiac volumes will be performed. This will conclude the invasive catheterization visit. The patient will be monitored per standard clinical protocols following right heart catheterization and discharged the same day.
- At a separate visit following cardiac catheterization, but prior to receipt of study drug, participants will have a QOL assessment, dual energy X-ray absorptiometry (DEXA), and measurement of plasma volume using the labelled albumin indicator dilution technique. Study coordinator will review patient preferences regarding contact during the study including video teleconference (preferred) or phone call.
- Patients will be randomized in a double-blind fashion to dapagliflozin 10 mg once daily or matching placebo. Study drug dispensed by research pharmacy.

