- Telephone visits will be conducted at 2 days, 1 week, 2 weeks, and then every 4 weeks thereafter, for a total of 24 weeks. One week after visit 4, there will be an additional telephone visit for safety after patient is no longer on study drug. All phone visits will have a window of +/- 3 days. Participants will be contacted by phone or through videoconference visits (based upon patient preference) to evaluate for AEs/SAEs, and encourage compliance with the study medication. Adverse events will be determined using a general approach, asking participants if there have been any changes to their overall health since the prior visit, including any unplanned hospital

Page 9 of 34

- or clinic visits. At 2 weeks, as part of standard of care, patients will undergo laboratory draw from complete blood count, electrolytes and renal function at their local lab, with results reviewed by the study teamIf needed, a physician on the trial can put in a referral order for the lab work.
- At the conclusion the 24 week treatment period, participants will return to complete the same invasive hemodynamic assessments and noninvasive assessments as described in steps (1) through (5) above (2 visits). Patient must remain on study drug through Visit 4, and may be on drug up to 7 days after the 24 week mark.
- 9) A follow up telephone/videoconference visit will be scheduled 1 week after completion of the trial to evaluate for AEs/SAEs following completion. This will have a window of +/- 3 days.

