After resting hemodynamic assessments have been performed, a 6 Fr MPA catheter will be advanced from the right internal jugular vein to the coronary sinus (CS) under fluoroscopic guidance, with CS location confirmed by oximetry (O₂ saturation<45%). Blood samples from the radial artery and CS will be drawn in triplicate (3 ml each) and averaged to measure blood gases (trans-myocardial O₂ uptake and CO₂ release based upon the difference between artery and CS tensions) along with glucose, lactate, triglyceride, pyruvate, ketone, and FFA uptake (total FFA and [U-¹³C]palmitate – enrichment in arterial and CS blood)). Additional mandatory research blood samples will be drawn frozen and stored for future discovery analysis. Samples will come from the CS, vein and artery once at the beginning of the procedure for future research. Samples will be transferred in iced tubes, centrifuged at 4°C and stored at -80°C for analysis.

Following resting metabolic assessments, participants will exercise at 20W workload on a supine ergometer for 3 minutes with the CS catheter in place, after which time arterial and CS sampling will be repeated during exercise in the same manner as at rest. The MPA catheter is then removed from the CS and exercise hemodynamic measurements are obtained. After obtaining exercise hemodynamic data at the 20W workload, workload is

increased in 20 W stages (3 minutes each) to volitional exhaustion. Hemodynamics and arterial and mixed venous blood samples are obtained at each stage.

Following exercise, catheters are removed and the patient is observed in the recovery area as per standard clinical practice prior to discharge.

6.2 Visit 2

At a second visit, typically the following day from the invasive catheterization can occur the day before visit 1 to allow flexibility, but no later than one week later, the patient will undergo plasma volume and blood volume assessment using the radiolabeled iodinated albumin ($^{131}\text{I},\,5{-}25~\mu\text{Cu}$) indicator dilution technique (BVA-100 Blood Volume Analyzer, Daxor Corp, NY) as is used clinically at Mayo Clinic and as we have described. 16 Patients will also undergo a DEXA scan in the Mayo CRTU.

At this visit QOL will be assessed using the SF-36 Questionnaire. Participants will receive the first 12 week supply of study drug as allocated in the randomization, and review study procedures and preferences for remote visits throughout the study period.

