6.3 Remote Telephone/Video Visits

Multiple visits will occur through videoconference (preferred) or telephone to assess for adverse events and ensure compliance with medication adherence. These visits will occur at the following timepoints: 2 day post procedure and 1, 2, 6, 10, 14, 18, & 22 weeks post procedure.

A final remote telephone/video visit will occur 1 week following the final on-site study visit to assess if there is any clinical change following discontinuation of study treatment.

6.4 Visits 3 & 4

These visits will be identical to visits 1 and 2, with the exception that study drug will be returned at the final on-site study visit.

Page 16 of 34

Test Schedule

Study Activity	V	isit 1	Visit 2	Visit 3	Visit 4
	Screen	Procedure	1-7 days following Visit 1 or 1 day prior to Visit 1	Week 24 (+/- 2 weeks)	1-7 days following Visit 3, or 1 day prior to Visit 3
Informed consent ¹	X		X		
History	X				
Concurrent meds	X		X	X	X
Physical exam (Ht, Wt, BSA, VS)	X			X	
Adverse event evaluation		X	X	X	X
NYHA Classification	X			X	
Blood Draw	X^2	X^3		X^1	
Serum pregnancy ⁴	X		X	X	
RHC		X		X	
Exercise study with hemodynamics		X		Х	
Blood gasses		X		X	
Limited Echo		X		X	
Blood volume test			X		X
SF-36 Questionnaire			X		X
DEXA			X		X

¹ Consent can occur on Visit 1 or Visit 2 and must occur before any research activities take place.

Page 17 of 34

² Pre-procedure: CBC, creatinine, BUN, sodium, potassium, aspartate aminotransferase, alanine aminotransferase, total, direct and indirect bilirubin, hsCRP, NTproBNP, and HgbA1c as part of clinical care

³ Research blood will be drawn, processed, stored and tested in [name] lab.

⁴ For women of childbearing potential, required to be done once before any research assessments, either Visit 1 or Visit 2.

DAPA/Placebo	X^5	X^5	X^6	X^6

⁵ 12 week supply dispensed once Visit 1 and Visit 2 are complete and 12 week supply mailed to patient at 12 weeks after remote visit

⁶ Study drug returned at either Visit 3 or 4, whichever is later

7 Statistical Plan

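### SF-36, blood volume and DEXA may fall before or after catheterisation at each time point, and nothing keeps a patient's order the same at baseline and week 24, which adds avoidable noise to exploratory change scores

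*Combined protocol and SAP*

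**What the plan says.** SF-36, the albumin-dilution plasma and blood volume test, and DEXA share one visit at each time point: Visit 2 at baseline and Visit 4 at week 24. Catheterisation with exercise is at Visits 1 and 3.

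- **Section 6.2** places Visit 2 as "typically the following day from the invasive catheterization can occur the day before visit 1 to allow flexibility, but no later than one week later". It adds: "At this visit QOL will be assessed using the SF-36 Questionnaire".
- **The Test Schedule** heads the Visit 2 column "1-7 days following Visit 1 or 1 day prior to Visit 1" and the Visit 4 column "1-7 days following Visit 3, or 1 day prior to Visit 3".
- **Section 3.1**, fifth step of the synopsis, allows one order only: "At a separate visit following cardiac catheterization, but prior to receipt of study drug, participants will have a QOL assessment". The week 24 step says that steps 1 to 5 are repeated over two visits.
- **Section 6.4** says of Visits 3 and 4: "These visits will be identical to visits 1 and 2", apart from the return of study drug.

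Section 3.5 lists plasma volume, blood volume, SF-36 and body composition as secondary exploratory endpoints. Objective 5 in section 2 will also "explore how these clinical changes relate to changes in hemodynamics, cardiac function, and cardiac metabolism".

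**The concern.** A change score is cleanest when both measurements are taken under the same conditions. Here the two conditions differ. One is the day before an invasive study with exercise to exhaustion and repeated blood sampling. The other is one to seven days after it. At baseline, a patient who returns after catheterisation can also infer that the wedge-pressure entry criterion was met (section 4.1); a patient seen the day before cannot.

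If a patient is measured after the procedure at baseline and before it at week 24, or the reverse, any difference between the conditions enters that patient's change score. The endpoints at stake are the SF-36 and plasma volume changes (objectives 5 and 4), with DEXA sharing the visit. In a trial planned for about 41 completers, noise that can be removed by a scheduling rule is worth removing.

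**Working it through.** **The plan's own figure.** The only power figure is in section 7.5: 93% for exercise PCWP with 18 per arm, a difference of 6 mmHg and SD 5 mmHg. The noncentrality is 6 / (5 × √(2/18)) = 3.6 on 34 degrees of freedom. At two-sided 0.05 this gives 93.8%, so the figure reproduces. It concerns PCWP measured at the catheterisation itself, and nothing below changes it.

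**What the passages permit**

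1. Visit 2 may fall at day −1 or days +1 to +7 relative to Visit 1 (section 6.2 and Test Schedule).
2. Visit 4 may fall at day −1 or days +1 to +7 relative to Visit 3 (Test Schedule). This choice is stated afresh, with no reference to the order used at Visit 2.
3. Four combinations are therefore allowed: after/after, before/before, after/before and before/after. The last two mix conditions. The interval can differ within a patient by up to 7 − (−1) = 8 days, or by up to 7 − 1 = 6 days even when both visits follow catheterisation.
4. Section 3.1 allows only the after order at baseline and so conflicts with the day-before option in section 6.2 and the Test Schedule.
5. Study drug is dispensed only once Visits 1 and 2 are both complete, and it continues through Visit 4. Either order is thus off drug at baseline and on drug at week 24.
6. Section 7.6 models actual time from baseline for outcomes with more than two replications. SF-36 and blood volume are scheduled twice, and time from baseline does not encode order relative to catheterisation. No order term or related sensitivity analysis is planned.

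**Illustration of size (all inputs assumed).** The documents give no SD and no order effect for these endpoints. Take the change-score SD as 1. Let q be the probability that the visit follows catheterisation, chosen independently at each time point, and s a constant order shift in SD units.

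- Proportion with discordant order: 2q(1 − q).
- Variance of the change score: V = 1 + s² × 2q(1 − q).
- Power by normal approximation, 20 per arm, two-sided 0.05, true effect 0.9 SD: Φ(0.9 / √(2V/20) − 1.96). With V = 1 this is Φ(2.846 − 1.96) = 81.2%.
- SD of the chance difference between arms due to order: s × √(2q(1 − q) × 2/20).

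| q | Discordant | s | Rise in variance | Power | SD of chance arm difference |
|---|---|---|---|---|---|
| 0.5 | 50% | 0.2 | 2.0% | 80.5% | 0.045 |
| 0.5 | 50% | 0.5 | 12.5% | 76.5% | 0.112 |
| 0.7 | 42% | 0.2 | 1.7% | 80.6% | 0.041 |
| 0.7 | 42% | 0.5 | 10.5% | 77.3% | 0.102 |
| 0.9 | 18% | 0.2 | 0.7% | 80.9% | 0.027 |
| 0.9 | 18% | 0.5 | 4.5% | 79.5% | 0.067 |

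If every patient keeps the same order, a constant shift cancels from the change score and these losses are zero.

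**The case against.** The strongest reply is that the default order already matches. Section 6.2 calls the following day typical, the synopsis places these tests after catheterisation and repeats the steps at week 24, and section 6.4 calls the later visits identical. The day-before slot is an exception for flexibility. On that reading q is near 0.9 or higher, and the loss of power is a fraction of a point unless the order shift is large. Most of this stands: switching may well be uncommon. It does not close the gap, because the Test Schedule offers the choice again at Visit 4 and neither general statement fixes a patient's order.

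It also stands that only exploratory endpoints are involved, that allocation is randomised and blinded, and that section 7 specifies no analysis of the relation between SF-36 and PCWP.

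A reader might infer three stronger points. The documents do not support them.

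- **That patients rate quality of life knowing their wedge result, which biases the SF-36/PCWP association or the comparison of arms.** No passage says that haemodynamic values are given to patients. The blinding section covers study drug only, so disclosure is neither stated nor ruled out. At baseline, having met the entry criterion is common to every randomised patient whose Visit 2 follows Visit 1.
- **That blood sampling distorts plasma volume.** The scheduled metabolic samples come to 3 mL × 3 replicates × 2 sites × 2 conditions = 36 mL, and further samples have no stated volume. The documents give no recovery time or assay variability, so no lasting effect one to seven days later can be shown.
- **That SF-36 clearly belongs in the isotope run-in of about 60 minutes.** Answering while cannulated and waiting for an invasive procedure is not a neutral condition either.

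**Conclusion.** The point holds as a minor but cheap improvement. Followed as written, the protocol lets one change score combine a pre-procedure and a post-procedure measurement, and its sections disagree on whether the pre-procedure option exists at baseline.

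The expected consequence is added noise and some chance imbalance in SF-36 and in plasma and blood volume, with DEXA exposed to the same scheduling. Systematic bias between arms is not expected, since order should be unrelated to allocation. The primary PCWP analysis is unaffected.

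The size cannot be derived from the documents. Under the assumed ranges, power for a 0.9 SD effect falls from 81.2% to between 80.9% and 76.5%. The lower end needs order to be a coin-flip and a 0.5 SD shift, and the word typical in section 6.2 makes a coin-flip unlikely. If patients happened to learn their week 24 result before completing SF-36, the exploratory SF-36/PCWP association could also be affected, but that rests on disclosure the documents do not describe.

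**What to change.** 1. Reconcile the fifth synopsis step in section 3.1 with section 6.2 and the Test Schedule, so that all three state the same permitted timing for Visit 2.
2. State in section 6.4 and in the Visit 4 column of the Test Schedule that SF-36, blood volume and DEXA are done in the same order relative to catheterisation as at that patient's Visit 2, and at a similar interval.
3. Record the order and the number of days from catheterisation on the case report form at both time points.
4. Add to section 7.6 a sensitivity analysis of these endpoints, either adjusted for order or limited to patients with concordant order.
5. Optionally, have SF-36 completed before catheterisation at both time points, after consent and ideally before cannulation. This would also remove any question of knowing the result.

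The cost of items 1 to 4 is a text change, two recorded fields, one extra analysis and slightly less scheduling freedom at Visit 4. Item 5 adds a questionnaire from patients who then fail screening: about 60 − 46 = 14 on the numbers in section 3.2. No visit is added.

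### Minor, patient safety only: the baseline 131-I blood volume test and DEXA may be done the day before the catheterisation that decides eligibility, even in patients whose exercise PCWP is unknown

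*Combined protocol and SAP*

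**What the plan says.** **Eligibility.** Section 4.1 item 6 requires an exercise PCWP of at least 25 mmHg, established at Visit 1. Patients who have consented but miss it are screen failures and are not randomised.

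**Timing in the operative text.** Section 6.2 puts the 131-I albumin blood volume test, the DEXA scan and the SF-36 at Visit 2. It describes the day after catheterisation as typical, allows up to a week, and adds that the visit "can occur the day before visit 1 to allow flexibility". The Visit 2 column of the Test Schedule gives the window as "1-7 days following Visit 1 or 1 day prior to Visit 1".

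**Timing in the synopsis.** Section 3.1 has only one order: "At a separate visit following cardiac catheterization, but prior to receipt of study drug", patients have the quality-of-life assessment, "dual energy X-ray absorptiometry (DEXA), and measurement of plasma volume using the labelled albumin indicator dilution technique".

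**Who is recruited.** Section 3.1 describes a mixed intake: "Some patients will have previously been identified and some will have be referred to the catheterization lab". The referred patients are being worked up for suspected HFpEF and qualify only if the haemodynamic criterion is met.

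**Safeguards for either order.** Three footnotes to the Test Schedule work whichever visit comes first:
- Footnote 1, consent: "Consent can occur on Visit 1 or Visit 2 and must occur before any research activities take place".
- Footnote 4, pregnancy testing: "required to be done once before any research assessments, either Visit 1 or Visit 2".
- Footnote 5, study drug: "12 week supply dispensed once Visit 1 and Visit 2 are complete".

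No footnote makes the 131-I test or DEXA wait for a qualifying PCWP.

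**The concern.** Both Visit 2 tests expose the patient to radiation for research purposes. For a patient with no earlier exercise catheterisation, Visit 1 is the first time anyone learns whether item 6 is met. Doing the tests the day before means doing them while entry to the trial is still open.

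A patient who then fails gains nothing from them, and neither does the trial. Blood volume and body composition are secondary exploratory endpoints (3.5 items 5 and 6), and 7.8 analyses subjects by randomised allocation. A baseline value from someone never randomised therefore enters no comparison. What is at stake is a small, avoidable exposure in some screen failures.

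**Working it through.** The plan states no figure for this point, so the check sets the sections side by side and then bounds the number of patients.

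**Step 1. Can the sequence occur?**
- Day -1: Visit 2 with the 131-I test and DEXA. Permitted by 6.2 and the Test Schedule, provided consent and any required pregnancy test come first (footnotes 1 and 4).
- Day 0: Visit 1 catheterisation. Exercise PCWP below 25 mmHg makes the patient a screen failure (4.1 item 6).
- Study drug: not dispensed, because the patient is not randomised and footnote 5 requires both visits to be complete.

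The sequence is allowed at every step. Nothing in 6.2 or the Test Schedule limits the slot to patients whose exercise PCWP is already known to qualify.

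**Step 2. How many patients?** Inputs: up to 60 consented and screened (3.2); 46 randomised (3.2, and the accrual figure in the Study Summary). Section 3.2 also prints 41 as the number to be randomised, which the Study Summary gives as completers. Both are carried through.

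Upper limit = screened - randomised:
- With 46 randomised: 60 - 46 = 14; 14/60 = 23.3%.
- With 41 randomised: 60 - 41 = 19; 19/60 = 31.7%.

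Either limit is reached only if every screened patient who is not randomised both used the day-before slot and failed after it. The documents give neither the share failing on PCWP nor the use of the slot, so the lower limit is 0.

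**Step 3. How large is the exposure?** Section 6.2 gives an administered 131-I activity of 5-25 (unit printed as μCu, read here as μCi). No absorbed dose is given for the 131-I test or for DEXA, so harm per patient cannot be calculated.

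**Step 4. What flexibility is involved?** The baseline window has 1 day before and 7 days after Visit 1, so 1 + 7 = 8 permitted days. Withholding the day-before slot removes 1 of 8 (12.5%) for the patients concerned. This counts days, not use: 6.2 calls the following day typical, so the days are not equally used.

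**Step 5. Does follow-up matter?** Section 6.4 models Visits 3 and 4 on Visits 1 and 2, and the Test Schedule gives Visit 4 the matching window. No eligibility question arises there. The order still bears on measurement, because plasma volume is compared before and after treatment. A patient tested after catheterisation at baseline and before it at follow-up would have a change in order around an invasive procedure with repeated blood sampling.

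**The case against.** The strongest reply is that the slot is deliberate. Section 6.2 gives flexibility as the reason, the Test Schedule carries it through both visit pairs, and three footnotes accommodate it. The only contrary text is 3.1, which is labelled a brief synopsis. This stands: a reader might infer a drafting error from the mismatch with 3.1, but the operative sections agree with each other. The point rests on 4.1, 6.2 and the Test Schedule, and 3.1 only needs aligning.

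A second reply is proportion. At Visit 1 the isotope infusion, the coronary sinus catheterisation under fluoroscopy and the blood sampling already precede the exercise haemodynamics, so every PCWP failure undergoes them. That is true, but they belong to the session in which the patient qualifies or fails. The 131-I test and DEXA do not, and can wait a day.

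A third reply is that few patients may be affected and that 6.2 describes the blood volume technique as one in clinical use. Both stand, and they keep the point minor.

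A fourth reply concerns the remedy. Banning the slot for everyone at baseline while leaving it at follow-up would stop patients from keeping the same order at both time points. It could also oblige someone already on site the day before to stay or come back, since patients go home on the day of catheterisation. This stands and argues against an outright ban.

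**Conclusion.** The point holds as a minor, inexpensive improvement to patient safety. A consented patient with no known exercise PCWP may have the research 131-I test and DEXA before the result that decides eligibility; if the patient fails, the exposure was avoidable.

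The number affected cannot be derived. It lies between 0 and at most 14 of 60 screened with 46 randomised, or 19 of 60 with 41 randomised, taking the planned counts at face value. Harm per patient is probably small, though the documents give no absorbed dose.

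The documents do not support three stronger readings that a reader might infer:
- That 14 or 19 patients are expected to be exposed. These are limits that assume full use of the slot by every patient who is not randomised.
- That the slot allows research procedures without consent or a required pregnancy test, or study drug for an ineligible patient. Footnotes 1, 4 and 5 and 4.1 item 6 rule these out.
- That the trial's conclusions are at risk. Power, randomisation and the primary PCWP analysis do not depend on when these two tests are done.

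**What to change.** - In 6.2 and the Visit 2 column of the Test Schedule, limit the day-before slot for the baseline 131-I test and DEXA to patients with a previously documented exercise PCWP of at least 25 mmHg. Sections 3.1 and 4.3 indicate that some recruits are already identified HFpEF patients, so the slot can keep a use.
- All other patients have these tests 1-7 days after a qualifying Visit 1.
- Align 3.1 with this rule, including the exception.
- Where practical, do Visit 4 in the same order relative to Visit 3 as Visit 2 was relative to Visit 1, so that the blood volume comparison is not affected by a change in order around catheterisation.

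**Cost.** Wording in 6.2, one column heading in the Test Schedule, a clause in 3.1 and a sentence on follow-up order. Patients without a prior qualifying PCWP lose the day-before option, and some may need to stay on or return after Visit 1. A small risk remains for those who keep the slot, because item 6 still requires the value at Visit 1 and a previously qualifying patient could fall short on the day.
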